6.5.3.11 Adrenal monitoring

Subjects were asked to undergo scheduled adrenal monitoring at the safety closeout visit. The adrenal monitoring comprises the following assessments:

- Adrenal gland imaging
- Laboratory testing
- Signs and symptoms suggestive of hypercortisolism, hyperaldosteronism

All tables generated within this adrenal monitoring section will contain the absolute number of subjects and percentage among subjects who performed the safety closeout visit.

An *overview* table will be provided. This table includes the number and percentage of subjects taking part at the specific adrenal monitoring assessments. The following numbers and percentages of subjects will be provided in addition:

- Subjects with abnormal result in at least one of the assessments.
- Subjects with abnormal result for each specific assessment separately.
- Subjects for whom an external expert recommendation was obtained. Among those, also the number and percentage of subjects with any findings suspicious of an adrenal disorder and recommendation for further handling will be provided.
- Subjects who have seen a local specialist (including information on type of specialist).

Details of the *final diagnosis by the expert panel* will be provided in another table. This table contains the number and percentage of subjects assessed by an expert, subjects needed expert panel meeting, subjects where expert panel met, and subjects with at least one diagnosis by the expert panel. Among those, the following numbers and percentages of subjects will be provided:

- Subjects with agreement of the diagnosis among all three experts.
- Subjects with a specific diagnosis (multiple diagnoses are possible).

A listing of subjects with other diagnosis (i.e. diagnosis entered by the expert panel in a text field) will be provided. A listing of subjects with adrenal tumor will be presented as well. It includes diagnosis, time from last study drug until date of panel assessment and possible causal relationship to study drug. Cases where the three experts did not agree on a diagnosis, are presented in a separate listing including also the diagnosis of the local specialist.

A third table will summarize the *diagnosis by a local specialist*. This table contains the number and percentage of subjects with at least one diagnosis by the local specialist. Among those, the numbers and percentages of subjects with a specific diagnosis (multiple diagnoses are possible) will be reported.

A listing of subjects with other diagnosis (i.e. diagnosis entered by a local expert in a text field) will be provided as well as a listing of reasons if a local specialist consultation did not take place despite referral.

A listing of local laboratory measurements will be provided (no descriptive analyses will be performed on those).

A table with *results of the adrenal glands imaging* will be provided. This table contains the number and percentage of subjects who did and who did not perform adrenal imaging (and reasons if not performed), and who have at least one evaluable image. Among subjects having performed adrenal glands imaging the type of procedure (e.g. CT scan with contrast) will be reported. The following numbers and percentages of subjects will be derived among subjects with at least one evaluable image:

- Subjects with one or two evaluable lateralities.
- Subjects with adrenal mass (if yes, in one or in both adrenal glands).
- Subjects with specified diagnostic benign imaging features.
- Subjects with specified indeterminate imaging features.

Reader results where an adjudicator was needed due to discrepant diagnoses between the two readers will be provided in a listing.

6.5.3.12 Skin monitoring

Findings resulting from skin monitoring will be analyzed descriptively by treatment group. All subjects who consent for safety follow-up and attend the Safety closeout visit will undergo a thorough skin examination by a dermatology expert. The information will be recorded on the eCRF assigned to the safety closeout visit. The analysis will show the number of subjects who consented to participate in the Safety Follow-up, how many were assessed by a dermatologist or other clinician, which diagnostic tests were used and the results of the assessment as follows: number of

normal and abnormal findings; and following an abnormal finding which type of abnormality as recorded in the eCRF: 'Precancerous skin lesion', 'Cutaneous sarcoma', 'Other malignant skin tumor' and 'Other skin abnormality'.

Relevant cases will be reported as AEs, potentially as an AESI, and a narrative will be written.

6.5.3.13 UF-DBD bleeding pattern per 28 days and 84 days based on UF-DBD

The bleeding data recorded on the UF-DBD will be summarized using descriptive statistics in the safety analysis set by treatment groups using time intervals C and time intervals D. A reference period of 28 days will be used for most analyses, which corresponds with the time interval D. When a reference period of 84 days is used the time intervals D will be modified accordingly.

The bleeding intensity will be summarized by bleeding category using frequency tables by reference period of 28 days and 84 days.

The maximum bleeding intensity will be summarized using frequency tables by 28 days reference period.

The number of bleeding days will be analyzed by 28 days reference period and with the following bleeding categories:

- non-bleeding,
- spotting-only,
- bleeding (category of bleeding intensity \geq mild)
- bleeding including spotting (category of bleeding intensity \geq spotting)
- mild
- moderate
- severe
- very severe

For the safety bleeding analysis, and in contrast with the analysis of efficacy variables based on bleeding data, bleeding induced by endometrial biopsies will not be excluded.

An incomplete period which does not comprise 28 (or 84, respectively) days will be analyzed for any of the considered time periods of Intervals C. The analysis of this incomplete period is based on all subjects for whom the length of the considered time period is not a multiple of 28 (or 84, respectively) days. Subject's data from the last $x < 28$ ($x < 84$) days of the considered time period will be included.

7. Subgroup analyses

Subgroups for endpoints as described in section 6.2.2 and 6.2.3.1

- 1) Subjects who fulfill the inclusion criteria of HMB > 80.00 mL by MP during screening period (depicted by Baseline Volume of menstrual blood loss per 28 days) and at least one fibroid > 3 cm at baseline by Ultrasound vs. subjects who did not fulfill these criteria at baseline.

8. Document history and changes in the planned statistical analysis

SAP version 1.0. dated 31 Jul 2017

9. References

1. Recording and Evaluation of Bleeding Data Version 6.0 (BHC-RD-OI-107)
2. Nikica Živković¹, Krešimir Živković², et al. Measuring the volume of uterine fibroids using 2- and 3- dimensional ultrasound and comparison with histopathology. Acta Clin Croat. 2012; 51:579-589

Appendix 1: Handling of Patient-report outcomes

UFS-QoL scores

To calculate a symptom score for symptom severity, create a summed score from the items listed below and then use the formula below the table to transform the value. This will provide symptom scores where higher score values are indicative of greater symptom severity or bother and lower scores will indicate minimal symptom severity (high scores= bad).

Table 9-1 Formula for calculating symptom score for symptom severity

Scale	Sum Item Values	Lowest and Highest Possible Raw Scores	Possible Raw Score Range
Symptom Severity	Sum 1-8	8, 40	32

Transformation for Symptom Severity raw scores ONLY:

$$\text{Transformed Score} = \frac{(\text{Actual raw score} - \text{lowest possible raw score})}{\text{Possible raw score range}} \times 100\%$$

For the HRQoL subscales (concern, activities, energy/mood, control, self-conscious, and sexual function), create summed scores of the items listed below for each individual subscale. To calculate the HRQoL total score, sum the value of each individual subscale (do not sum individual items). Use the formula below the table to transform all values. Higher scores will be indicative of better HRQoL (high = good).

Table 9-2 Formula for calculating HRQoL subscales and total score

Scale	Sum Item Values	Lowest and Highest Possible Raw Scores	Possible Raw Score Range
Concern	9+15+22+28+32	5,25	20
Activities	10+11+13+19+20+27+29	7,35	28

Energy/mood	12+17+23+24+25+31+35	7,35	28
Control	14+16+26+30+34	5,25	20
Self-conscious	18+21+33	3, 15	12
Sexual function	36+37	2, 10	8
HRQoLTOTAL	Sum of 6 Subscale Scores	29, 145	116
Revised activities	11+13+19+20+27	5,25	20
Revised HRQLTOTAL	Sum of 6 Subscale Scores (replacing activities with revised activities)	27,135	108

Formula for transformation of HRQoL raw scores ONLY:

$$\text{Transformed Score} = \frac{(\text{Highest possible score} - \text{Actual raw score})}{\text{Possible raw score range}} \times 100\% \text{Missing Items}$$

For the subscale analyses, if < 50% of the scale items are missing, the scale should be retained with the mean scale score of the items present used to impute a score for the missing items. If ≥ 50% of the items are missing, no scale score should be calculated, the subscale score should be considered missing. If a subscale score is missing, the HRQoL total cannot be calculated.

Appendix 2 : The maximum or minimum measurement for laboratory parameters

Table 9-3 The maximum or minimum measurement for laboratory parameters

Laboratory category	Laboratory test	lowest	highest
VITAMINS	25-Hydroxyvitamin D	X	
COAGULATION	Activated Partial Thromboplastin Time		X
HORMONES	Adrenocorticotrophic Hormone	X	X
GENERAL CHEMISTRY	Alanine Aminotransferase		X
GENERAL CHEMISTRY	Albumin	X	
GENERAL CHEMISTRY	Alkaline Phosphatase		X
IMMUNOLOGY	Alpha-1 Antitrypsin		X
IMMUNOLOGY	Anti Mitochondrial Antibody		X
IMMUNOLOGY	Antinuclear Antibodies		X
GENERAL CHEMISTRY	Aspartate Aminotransferase		X
HEMATOLOGY	Basophils	X	X
HEMATOLOGY	Basophils/Leukocytes		X
GENERAL CHEMISTRY	Bilirubin		X
URINALYSIS	Bilirubin		X
URINALYSIS	Blood		X
GENERAL CHEMISTRY	Bone Specific Alkaline Phosphatase		X
MICROBIOLOGY	Brucellae		X
GENERAL CHEMISTRY	Calcium	X	X
PROTEINS	Ceruloplasmin		X
GENERAL CHEMISTRY	Chloride		X
GENERAL CHEMISTRY	Cholesterol		X
	Choriogonadotropin Beta		X
HORMONES	Choriogonadotropin Beta		X

URINALYSIS	Choriogonadotropin Beta		X
HORMONES	Cortisol	X	X
GENERAL CHEMISTRY	Creatine Kinase		X
GENERAL CHEMISTRY	Creatinine		X
IMMUNOLOGY	Cytomegalovirus DNA		X
GENERAL CHEMISTRY	Direct Bilirubin		X
HEMATOLOGY	Eosinophils		X
HEMATOLOGY	Eosinophils/Leukocytes		X
IMMUNOLOGY	Epstein-Barr Capsid IgG Antibody		X
IMMUNOLOGY	Epstein-Barr Capsid IgM Antibody		X
IMMUNOLOGY	Epstein-Barr Nuclear Antigen 1 IgG Ab		X
HEMATOLOGY	Ery. Mean Corpuscular Hemoglobin		X
HEMATOLOGY	Ery. Mean Corpuscular Volume	X	
HEMATOLOGY	Erythrocytes	X	
HORMONES	Estradiol	X	
GENERAL CHEMISTRY	Ferritin	X	
HORMONES	Follicle Stimulating Hormone		X
GENERAL CHEMISTRY	Gamma Glutamyl Transferase		X
URINALYSIS	Glucose		X
IMMUNOLOGY	HCV PCR Viral Load		X
GENERAL CHEMISTRY	HDL Cholesterol	X	X
HEMATOLOGY	Hematocrit		X
HEMATOLOGY	Hemoglobin	X	
GENERAL CHEMISTRY	Hemoglobin A1C		X
IMMUNOLOGY	Hepatitis A Virus Antibody		X
IMMUNOLOGY	Hepatitis A Virus Antibody IgM		X
IMMUNOLOGY	Hepatitis B Virus Core Antibody		X
IMMUNOLOGY	Hepatitis B Virus DNA		X
IMMUNOLOGY	Hepatitis B Virus Surface Antibody		X
IMMUNOLOGY	Hepatitis B Virus Surface Antigen		X
IMMUNOLOGY	Hepatitis C Virus Antibody Surface		X
IMMUNOLOGY	Hepatitis D Virus Antibody		X
IMMUNOLOGY	Hepatitis D Virus IgG Antibody		X
IMMUNOLOGY	Hepatitis D Virus IgM Antibody		X
IMMUNOLOGY	Hepatitis D Virus RNA		X
IMMUNOLOGY	Hepatitis E Virus Antibody		X
IMMUNOLOGY	Hepatitis E Virus IgG Antibody		X
IMMUNOLOGY	Hepatitis E Virus IgM Antibody		X
IMMUNOLOGY	Hepatitis E Virus RNA		X
IMMUNOLOGY	Herpes Simplex Virus 1 IgG Antibody		X
IMMUNOLOGY	Herpes Simplex Virus 1 IgM Antibody		X
IMMUNOLOGY	Immunoglobulin A		X
IMMUNOLOGY	Immunoglobulin G		X
IMMUNOLOGY	Immunoglobulin M		X
GENERAL CHEMISTRY	Iron	X	
URINALYSIS	Ketones		X
GENERAL CHEMISTRY	Lactate Dehydrogenase		X
GENERAL CHEMISTRY	LDL Cholesterol		X
MICROBIOLOGY	Leptospirae		X
HEMATOLOGY	Leukocytes	X	
URINALYSIS	Leukocytes		X
HORMONES	Luteinizing Hormone		X
HEMATOLOGY	Lymphocytes	X	
HEMATOLOGY	Lymphocytes/Leukocytes		X
HEMATOLOGY	Monocytes	X	
HEMATOLOGY	Monocytes/Leukocytes		X
IMMUNOLOGY	MPO ANCA		X
HEMATOLOGY	Neutrophils	X	
HEMATOLOGY	Neutrophils/Leukocytes		X
URINALYSIS	Nitrite		X
GENERAL CHEMISTRY	Osteocalcin		X

HEMATOLOGY	Platelets	X	
GENERAL CHEMISTRY	Potassium	X	x
IMMUNOLOGY	PR3 ANCA		X
HORMONES	Progesterone	X	
HORMONES	Prolactin		X
GENERAL CHEMISTRY	Protein		X
URINALYSIS	Protein		X
COAGULATION	Prothrombin Intl. Normalized Ratio	X	
COAGULATION	Prothrombin Time		X
GENERAL CHEMISTRY	Pseudocholinesterase		X
IMMUNOLOGY	Smooth Muscle Antibody		X
GENERAL CHEMISTRY	Sodium	X	
HORMONES	Testosterone		X
HORMONES	Thyrotropin	X	X
GENERAL CHEMISTRY	Time to event		X
GENERAL CHEMISTRY	Total Iron Binding Capacity		X
IMMUNOLOGY	Toxoplasma gondii antibody		X
GENERAL CHEMISTRY	Triglycerides		X
GENERAL CHEMISTRY	Type I Collagen C-Telopeptides		X
URINALYSIS	Urobilinogen		X
	all parameters not otherwise specified		X

Appendix 3 : List of AESIs in current expert statement based on MedDRA Version 22.1 (version 5.0, status 2020-02-19)

Table 9-4 List of AESIs

#	AESI	Grouping
1	HMB (especially after end of treatment): HMB will be documented in detail throughout the study	MTG: [BMQ] Increased female genital bleeding[V8]
2	Progesterone receptor modulator-associated endometrial changes (PAEC) (not an AESI in 16953)	PT selection: PT: Endometrial thickening PT: Endometrial disorder PT: Endometrial hypertrophy PT: Biopsy endometrium abnormal PT: Biopsy uterus abnormal
3	Ovarian cysts (), not an AESI in study 16953)	MTG: [BMQ] Benign ovarian cyst and associated complications[V21]
4	Liver enzymes	SMQ: Drug related hepatic disorders - comprehensive search (SMQ)[V29]
5	Endometrial hyperplasia (all subcategories according to WHO 2014 (and WHO 1994) classification	PT selection: PT: Endometrial hyperplasia PT: Biopsy endometrium abnormal PT: Endometrial dysplasia PT: Endometrial metaplasia

		PT: Biopsy uterus abnormal
6	Endometrial thickening >18 mm	
PT selection:
 
PT: Endometrial thickening PT: Endometrial disorder PT: Endometrial hypertrophy

7	Loss of BMD	
SMQ: Osteoporosis/osteopenia (SMQ) (V21)

8	Adrenal neoplasms, Adrenal diagnoses related to cortical hyperfunction and cortical hypofunction	
PBMQ: Adrenocortical gland pathology including tumors and related hormonal changes and conditions vilaprisan(narrow scope)
 
PT Addison's disease PT Adrenal adenoma PT Adrenal androgen deficiency PT Adrenal atrophy PT Adrenal calcification PT Adrenal cortex dysplasia PT Adrenal cortex necrosis PT Adrenal cyst PT Adrenal disorder PT Adrenal gland abscess PT Adrenal gland cancer PT Adrenal gland cancer metastatic PT Adrenal gland injury PT Adrenal gland tuberculosis PT Adrenal glomerular zone abnormal PT Adrenal haematoma PT Adrenal haemorrhage PT Adrenal insufficiency PT Adrenal insufficiency neonatal PT Adrenal mass PT Adrenal neoplasm PT Adrenal suppression PT Adrenal thrombosis PT Adrenalitis PT Adrenocortical carcinoma PT Adrenocortical insufficiency acute PT Adrenocortical insufficiency neonatal PT Adrenogenital syndrome PT Adrenoleukodystrophy PT Adrenomegaly PT Benign neoplasm of adrenal gland PT Catecholamine crisis PT Congenital adrenal gland hypoplasia PT Congenital anomaly of adrenal gland PT Cortisol deficiency PT Cushingoid PT Cushing's syndrome PT Familial glucocorticoid deficiency PT Glucocorticoid deficiency PT Haemorrhagic adrenal infarction PT Hyperadrenalism PT Hyperadrenocorticism PT Hyperaldosteronism PT Hypercorticism PT Hypoaldosteronism PT Metastases to adrenals PT Mineralocorticoid deficiency

		PT Myelolipoma PT Primary adrenal insufficiency PT Primary hyperaldosteronism PT Pseudohypoaldosteronism PT Secondary adrenocortical insufficiency PT Secondary aldosteronism PT Steroid withdrawal syndrome PT Triple A syndrome
9	Cutaneous sarcomas	PT selection: PT: Dermatofibrosarcoma protuberans PT: Atypical fibroxanthoma PT: Leiomyosarcoma PT: Liposarcoma PT: Skin angiosarcoma PT: Kaposi's sarcoma PT: Malignant fibrous histiocytoma PT: Soft tissue sarcoma

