6.5.3.6 Laboratory parameters

For immunology and coagulation parameters Intervals ‘BL/Post baseline’ will be used, while for all other laboratory measurements the following time intervals will be considered:

- Intervals C (according to Figure 4-1)

The tabulation will follow in principle the Bayer Global Standard Tables catalogue (currently V 4.0 default), with the necessary modifications like for time interval presentation instead of visit presentation.

The maximum or minimum measurement within the time interval will be used for calculations, following a worst-case approach (for details please refer to Appendix 2). Scheduled as well as unscheduled measurements will be considered.

Central as well as local lab measurements are available. Summary statistics will be provided based on central lab. Local lab measurements will be listed.

Values below the lower limit of quantification (LLOQ) will be set to LLOQ/2.

Values above the upper limit of quantification (ULOQ) will be set to ULOQ.

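### Table 9-3 takes the highest mean corpuscular hemoglobin and the highest hematocrit as the worst case, against the direction set for the related red-cell and iron tests

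*SAP*

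**What the plan says.** SAP section 6.5.3.6 sets the rule: "The maximum or minimum measurement within the time interval will be used for calculations, following a worst-case approach (for details please refer to Appendix 2"). It adds: "Scheduled as well as unscheduled measurements will be considered". An interval can therefore hold more than one value for the same test.

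Appendix 2, Table 9-3, then marks each test *lowest*, *highest* or both. The rows that matter here are:

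| Test | Marked |
|---|---|
| Hemoglobin | lowest |
| "Erythrocytes" | lowest |
| "Ery. Mean Corpuscular Volume" | lowest |
| Ferritin | lowest |
| Iron | lowest |
| Total iron binding capacity | highest |
| "Ery. Mean Corpuscular Hemoglobin" | **highest** |
| Hematocrit | **highest** |
| Prothrombin time | highest |
| INR | **lowest** |
| Albumin | lowest |
| Protein (general chemistry) | highest |
| "Pseudocholinesterase" | highest |

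The last row sends "all parameters not otherwise specified" to *highest*. Some tests, such as calcium and potassium, are marked in both columns, so a two-sided option exists in the table.

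Section 6.2.3.6.1 lists hemoglobin, hematocrit and ferritin as efficacy variables and refers their analysis to section 6.5.3.6. Section 6.2.3.6.2 treats hemoglobin above 12 g/dL and hematocrit above 36% as normal. Section 6.2.3.6.3 counts subjects with hemoglobin of 10.9 g/dL or less.

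**The concern.** Most red-cell and iron rows treat iron-deficiency anemia as the adverse state. Counts, cell size and iron stores are taken at their lowest, and iron binding capacity, which rises in iron deficiency, at its highest. MCH falls with MCV in that condition, yet it is taken at its highest. The SAP gives no reason for the exception.

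The output headed as a worst case would then show MCV at its lowest and MCH at its highest within the same interval, and the two would describe opposite extremes. The same happens with hemoglobin and hematocrit, both of which are named efficacy variables. A reader of the tables could take the result for a real divergence between indices, or could miss a short-lived fall.

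**Working it through.** The SAP states no figure for this point, so there is none to reproduce. The check has two parts.

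**1. Direction, row against row**

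- *MCH against MCV.* These are adjacent rows with opposite marks. If high values were the concern for red-cell indices, MCV would also be *highest*. If both sides mattered, both columns could have been marked, as for calcium.
- *Hematocrit against hemoglobin.* The marks are opposite, although section 6.2.3.6.1 sends both to the same laboratory rule and section 6.2.3.6.2 sets a lower bound of normal for each (above 36% and above 12 g/dL). The SAP itself thus treats low hematocrit as the unfavourable side, and the *highest* mark contradicts that. Section 6.2.3.6.2 does not say which value in an interval decides normality. If the Table 9-3 value is used, hematocrit is judged on its best value and hemoglobin on its worst.
- *INR against prothrombin time.* The two move together, yet one is *lowest* and the other *highest*. Both cannot be the worst case for the same concern.
- *Table extraction.* Rows marked *lowest* only, *highest* only and both can all be told apart in the text, so the MCH mark is not a displaced column.

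**2. Size of the effect on a reported value**

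Inputs: k values of one test in one interval for one subject, assumed independent and normal around a constant mean, with within-subject SD s. The SAP gives neither k nor s, so k = 1 to 4 is an assumed range.

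Expected highest minus expected lowest:

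- k = 1: 0
- k = 2: 2s/√π = 2s/1.7725 = 1.13s
- k = 3: 3s/√π = 3s/1.7725 = 1.69s
- k = 4: 2.06s (simulation, 1,000,000 draws)

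The simulation gave 1.129, 1.693 and 2.058 for k = 2, 3 and 4, in agreement with the formulas.

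For change from baseline, section 4.5 takes a single last value before the reference start date as baseline. With no true change, the highest post-baseline value lies above the subject's mean by half the range: 1.13s/2 = 0.56s for k = 2 and 1.69s/2 = 0.85s for k = 3. For MCH and hematocrit this leans towards apparent improvement. Marking *lowest* would lean by the same amount towards deterioration, which is what a worst-case summary is meant to do.

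**The case against.** The case for leaving this alone is that the effect is small. MCH is a routine laboratory parameter, summarised descriptively, and is neither the primary safety variable (lumbar spine BMD) nor the secondary efficacy variable (number of bleeding days). Hemoglobin and ferritin are marked *lowest*, so a fall in either is still captured. An interval with one sample is unaffected. The rule is the same in all four groups, so with similar sampling the shift would be similar across them, and no biased group comparison is shown. All of this stands. It limits the importance of the point but does not make the marks right.

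A reader might draw three stronger conclusions that the document does not support.

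- *That a decline is hidden.* A fall that persists through the interval also lowers the highest value and remains visible. Only a transient fall is understated.
- *That a key anemia endpoint is wrong because of MCH.* The named anemia-related variables are hemoglobin, hematocrit and ferritin. The concern reaches a named variable through hematocrit.
- *That total protein and pseudocholinesterase are also wrong.* Both can fall when liver synthesis is impaired, but the SAP never says that low is the adverse side for either. Section 6.5.3.10 on liver monitoring names only ALT, AST, alkaline phosphatase and bilirubin. Albumin at *lowest* is a hint for total protein and establishes nothing for pseudocholinesterase. These two are queries.

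The catch-all row set to *highest* may suggest that MCH was left at a default. That is plausible but cannot be shown, since MCH has its own row.

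**Conclusion.** The point holds as a minor inconsistency. Table 9-3 reverses the worst-case direction for MCH relative to hemoglobin, erythrocytes, MCV, ferritin and iron, and nothing in the SAP justifies it. Hematocrit has the same reversal and is the more consequential row. The INR and prothrombin time marks conflict.

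For an interval with two or three samples, the reported MCH or hematocrit differs on average by 1.13 or 1.69 within-subject SD from what the opposite mark would give. This assumes independent normal values, and positive correlation between samples would shrink it. With one sample the difference is zero. The size in laboratory units cannot be given from the SAP. The judgement that low MCH is adverse rests on its relation to MCV and on the direction of the neighbouring rows, since the SAP does not state it for MCH itself.

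**What to change.** In Appendix 2, Table 9-3:

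1. Mark MCH *lowest*, or both columns.
2. Mark hematocrit *lowest*, or both columns, so that it agrees with hemoglobin and with the lower bounds in section 6.2.3.6.2.
3. Reconcile INR with prothrombin time so that both follow the same concern, or mark both columns for each.
4. Confirm the intended direction for general-chemistry protein and pseudocholinesterase, or mark both columns.

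The cost is one cell each for MCH, hematocrit and the INR or prothrombin time row if a single direction is chosen, a second mark in the row where both columns are used, and two rows to confirm. No new data are needed. The affected laboratory summaries have to be programmed, or rerun, with the corrected direction.

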In general, the last valid, non-missing value prior to the Reference start date will be considered as baseline value. For variables analyzed by 28-day periods, the baseline period corresponds to the last 28 days before the reference start date. This definition does not apply to analyses related to menstrual blood loss where a specific definition for baseline menstrual blood is defined (see baseline menstrual blood loss for 28 days).

Bleeding caused by conducting endometrial biopsy

If an endometrial biopsy was conducted, bleeding on the day of intervention and the 3 days thereafter will not be considered in the bleeding related evaluation, i.e., bleeding/spotting on the day of biopsy and 3 days thereafter will not be considered as day(s) with bleeding/spotting and MP values will be set to 0 mL. This rule is applicable for all bleeding related efficacy analyses.

A biopsy will be regarded as conducted if the intervention was attempted, either successfully or unsuccessfully. Successful means that the date of biopsy is given and 'Biopsy sample obtained - Not done' is not ticked in the eCRF. Unsuccessful means that the date of biopsy is given, 'Biopsy sample obtained - Not done' is ticked in the eCRF, and the reason 'Unsuccessful attempt' is selected.

Baseline menstrual blood loss for 28 days

Baseline menstrual blood loss for 28 days is defined as the sum of volume of menstrual blood loss data of respective days in the baseline cycle. If baseline cycle length is more than 28 days, only data from the first day of cycle to the 28th day of cycle will be used. If baseline cycle length is less or equal than 28 days, data from the first day of cycle to the last day of cycle will be used.

Baseline menstrual cycle

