6.2.3.6 Variables related to laboratory parameters

6.2.3.6.1 Change from baseline in hemoglobin, hematocrit, and ferritin

Hemoglobin, hematocrit, and ferritin will be analyzed in the same way as laboratory measurements described in section other safety variables (see section 6.5.3.6)

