6.2.3.6.2 Percentage of subjects with normal hemoglobin >12 g/dL and normal hematocrit >36%

Frequency tables with number of observations and percentage will be displayed by treatment period within treatment group and by Intervals C. A listing will be provided.

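### SAP Table 9-3 sets the worst-case direction the wrong way round for hematocrit and INR

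*SAP*

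**What the plan says.** Section 6.5.3.6 gives the selection rule: "The maximum or minimum measurement within the time interval will be used for calculations, following a worst-case approach". Scheduled and unscheduled values both count, and the direction for each parameter is in Table 9-3, which has a lowest and a highest column.

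- **Hematocrit.** The row is "HEMATOLOGY Hematocrit X", with the mark under highest. The next row, "HEMATOLOGY Hemoglobin X", has its mark under lowest, as do erythrocytes and ferritin.
- **INR.** The row is "COAGULATION Prothrombin Intl. Normalized Ratio X", with the mark under lowest. The next row, "COAGULATION Prothrombin Time X", has its mark under highest, as does aPTT.
- **Use as efficacy variables.** Section 6.2.3.6.1 states: "Hemoglobin, hematocrit, and ferritin will be analyzed in the same way as laboratory measurements". The heading of 6.2.3.6.2 sets the favourable side: "normal hemoglobin >12 g/dL and normal hematocrit >36" (percent).
- **Baseline.** Section 4.5 says that in general "the last valid, non-missing value prior to the Reference start date will be considered as baseline value".

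Two other rules also turn on direction. Section 6.2.3.5.2 summarises raw and transformed UFS-QoL scores and takes the lowest HRQoL score in the interval as the worst. In 6.5.3.4, the second definition of cyst resolution requires that no structure of 3 cm or less is seen, whereas the end-of-episode sentence after it counts a structure of 3 cm or less as resolved.

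**The concern.** Because Table 9-3 decides which measurement enters each summary, a mark in the wrong column selects the wrong data. On the SAP's own criteria a low hematocrit is unfavourable, yet the table keeps the highest. Hemoglobin and hematocrit are reported together in 6.2.3.6.1 but selected at opposite ends, so they could appear to move apart with no real change in either.

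INR is by name the normalised prothrombin measure, so it should not be worst at the opposite end from prothrombin time. Section 6.5.3.6 uses a single post-baseline interval for coagulation. One lowest INR therefore stands for the whole period after baseline, and a transient rise disappears from that summary.

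**Working it through.** **1. Could the marks be intended, or be an artefact of text extraction?** Where both sides matter, the table marks both columns (calcium, cortisol, potassium, thyrotropin). Hematocrit and INR each carry one mark. The two-mark rows are intact and adjacent rows keep distinct column positions, so a column shift is unlikely.

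**2. Size for hematocrit.** The SAP gives neither the number of values per interval nor the within-subject SD. Assume n = 1 to 4 independent normal values around a constant subject mean. In within-subject SDs:

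| n | Expected maximum above subject mean | Expected maximum minus minimum |
|---|---|---|
| 1 | 0 | 0 |
| 2 | 0.564 | 1.128 |
| 3 | 0.846 | 1.693 |
| 4 | 1.029 | 2.059 |

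Against a single-value baseline, an unchanged hematocrit would seem to rise by 0.56 to 1.03 SD (n = 2 to 4). An unchanged hemoglobin would seem to fall by 0.56 to 1.03 of its own SDs.

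**3. The 36% table, only if it uses the Table 9-3 value.** Section 6.2.3.6.2 does not say which value enters. With p the chance that one value exceeds the cut, P(maximum > cut) = 1 − (1 − p)^n and P(minimum > cut) = p^n. For n = 2 / 3 / 4:

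| Subject mean | p | By maximum | By minimum |
|---|---|---|---|
| 1 SD below cut | 0.159 | 0.292 / 0.404 / 0.499 | 0.025 / 0.004 / 0.0006 |
| At cut | 0.5 | 0.750 / 0.875 / 0.938 | 0.250 / 0.125 / 0.063 |
| 1 SD above cut | 0.841 | 0.975 / 0.996 / 0.999 | 0.708 / 0.596 / 0.501 |

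**4. INR.** For an invented series 1.0, 1.0, 2.0, 1.1, the lowest reports 1.0 and the highest reports 2.0.

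**5. HRQoL raw scores.** Appendix 1 transforms as (highest possible − raw) / range × 100. For the total, raw 29 gives (145 − 29)/116 × 100 = 100 (best) and raw 145 gives (145 − 145)/116 × 100 = 0 (worst). The same reversal holds in all nine rows of Table 9-2. The lowest value is thus the worst transformed score but the best raw score.

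**6. Cyst resolution.**

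| Structure seen | Second definition, read literally | End-of-episode sentence |
|---|---|---|
| None | resolved | resolved |
| 2 or 3 cm | not resolved | resolved |
| 4 or 5 cm | resolved | not resolved |

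The two agree only when no structure is seen.

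**The case against.** The marks themselves are not in dispute; the case against concerns size and weight.

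- **No effect with one value per interval.** This stands. The SAP gives no count, so 2 to 4 is an assumption, although unscheduled values are included.
- **Part of the apparent change belongs to the worst-case method.** This stands. With a single-value baseline, selecting the lowest hematocrit would give a spurious fall as large as the spurious rise. The wrong direction accounts for the maximum-minus-minimum gap and for the opposite movement against hemoglobin.
- **The rule applies to every group, so the shift is largely common.** This is fair if the groups have similar numbers of values per interval, which the SAP does not show. In any case it does not make a within-group table labelled worst case correct.
- **The 36% figures are conditional.** This stands, and they carry no weight in the conclusion.
- **The outputs are minor.** They are descriptive, and hemoglobin, erythrocytes, ferritin, prothrombin time and aPTT point the expected way, so a signal of anemia or altered coagulation is not lost altogether. INR is not among the liver-monitoring parameters in 6.5.3.10.
- **The HRQoL and cyst points are slight.** This stands. The HRQoL slip needs more than one questionnaire in a 28-day interval, and the end-of-episode sentence makes the intended cyst rule clear.
- **Other rows may be wrong too.** Mean corpuscular hemoglobin is marked highest beside mean corpuscular volume marked lowest. That is less clear-cut, but it argues for checking the whole table.

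**Conclusion.** The concern holds. The hematocrit and INR marks contradict the worst-case rule they implement, the related rows of the same table and, for hematocrit, the SAP's own criterion of normality.

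Where an interval has several values, the most favourable one is reported as the worst. For hematocrit the gap averages 1.13 to 2.06 within-subject SDs, assuming 2 to 4 independent normal values with a constant subject mean, and it is zero with one value. No general size can be given for INR from the SAP.

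This should be corrected, but its reach is limited to descriptive laboratory and other efficacy summaries. The raw HRQoL and cyst points are genuine but minor.

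**What to change.** - **Table 9-3:** move the hematocrit mark to lowest and the INR mark to highest. Check the direction of every other row at the same time, including mean corpuscular hemoglobin.
- **6.2.3.6.2:** state which value per interval enters the 36% table.
- **6.2.3.5.2:** choose the worst HRQoL record on the transformed score (equivalently, the highest raw score) and report that record's raw score with it.
- **6.5.3.4:** reword the second definition so that a cyst counts as resolved once no structure of that type larger than 3 cm remains in that ovary, in line with the end-of-episode sentence.

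The cost is two table cells, three sentences and a read through the table. No new data are needed, and the primary BMD and bleeding-day analyses do not change. Section 4.6 already provides for a SAP amendment or supplement. If the tables have already been programmed, which the SAP does not show, the affected summaries would have to be rerun.
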